## **2.4.2 Prior, concomitant and post therapies**

Analyses described in this section will be performed on the SAF.

### **2.4.2.1 Prior and Concomitant medication**

Records on the Concomitant Medications CRF page will be coded using the WHO drug dictionary. All medications will be classified as prior, concomitant or post study treatment discontinuation medication as follows:

- Prior medications are defined as drugs taken and stopped prior to first dose of study medication.
- Concomitant medications are defined as drugs taken at least once between the first and last dose of study medication (including those which were started prior to first dose and continued into the treatment period).
- Post-study treatment discontinuation medications are defined as drugs started after the discontinuation of study medication.

Medications will be categorized into one (and only one) of the above classes based on recorded or imputed start and end dates. When incomplete or missing, dates will be imputed according to Novartis standards (details will be given in programming datasets specifications (PDS) document). If both the start date and the end date are completely missing and medication has not been collected on the “Previous MS Disease Modifying Treatment” page, the medication will be classified into concomitant medication category.

Medications in each of these three categories will be summarized separately, Anatomical Therapeutic Chemical (ATC) code and preferred term. ATC level 1 and level 3 (e.g. M [Musculo-skeletal system], M01A [anti-inflammatory and anti-rheumatic products, non-steroids], etc.) will be used.

Data collected from the Previous MS disease modifying treatment pages will not be included in this summary.

### **2.4.2.2 Surgical and medical procedures**

Records on the Prior or Concomitant non-drug therapies/procedures CRF page will be coded using the MedDRA dictionary. All procedures will be classified as prior, concomitant or post-study treatment discontinuation procedure, in the same way as done for concomitant medications. Surgical and medical procedures in each of these three categories will be summarized separately by system organ class and preferred term (and/or listed, if appropriate).

Imputation rules for start and end dates will be the same as for the concomitant medications.

### **2.4.2.3 Injection related premedication**

Injection related premedication will be identified by subcategory “Injection related premedication” in concomitant medication data set. Injection related premedication will also be summarized separately for each injection up to injection 5 and cumulatively for injections after injection 5 (i.e., injections 6 to last injection) as well as cumulatively for all injections.

For injection 1 summary, the injection related premedication with either start date or end date on the same day as the first injection date will be included and summarized for each of the three protocol specified types and for each combination of the specified types (type 1+ type 2, type 1+ type 3, type 2+ type 3, type 1+ type 2+ type 3). The three protocol specified types are steroids (type 1), antihistamines (type 2), and antipyretics/analgesics (type 3). The steroids (type 1) will be identified by category “Steroid”. The antihistamines (type 2) will be identified by ATC level 3 “antihistamines for systemic use”. The antipyretics/analgesics (type 3) will be identified by ATC level 3 “other analgesics and antipyretics” and “anti-inflammatory and anti-rheumatic products, non-steroids”. In summaries for each combination of the specified types, the number and proportion of participants who took both or all 3 types of injection related premedication at specified injection will be provided.

Rest injection specific summaries or cumulatively summaries will be reported similarly.

#### **2.4.2.4 Previous MS disease modifying treatment**

MS medication history of previous disease-modifying drugs (coded by WHO drug dictionary) will be summarized by preferred term (PT) and treatment group. The number and proportion of treatment-naïve participants (i.e., participants who have not been treated with any disease-modifying drug before first dose of ofatumumab) will also be presented.

### **2.5 Analysis supporting primary objective(s)**

All analyses for primary objective will be conducted using the FAS.

#### **2.5.1 Primary endpoint(s)**

The primary endpoint is the annualized relapse rate (ARR), which is defined as the average number of confirmed MS relapses in a year (i.e. the total number of confirmed relapses, divided by the total days in the study, multiplied by 365.25). In the primary analysis, the ARR is estimated in a negative binomial (NB) model by using individual confirmed relapse count as the response variable, with time in study as an offset variable.

Two variables are required for the calculation of the ARR (excluding covariates):

- The cumulative number of confirmed MS relapses by subject is the response variable in the negative binomial model. All confirmed relapses with a start date on or after the date of first administration of study drug and prior to or on the end of treatment period date will be included in the analysis. Additional details are provided in [Section 5.1.4](#).
  - The definition of a confirmed MS relapse is one accompanied by a clinically relevant change in the EDSS assessment, i.e. an increase of at least 0.5 points on the EDSS (total) score, or an increase of at least 1 point on at least two Functional scores (FSs), or an increase of at least 2 points on at least one FS, excluding changes involving bowel/bladder or cerebral FS, compared to the last EDSS assessment taken in the absence of (confirmed or unconfirmed) relapse and prior to the current relapse. EDSS obtained on the date as indicated on the Summary of MS Relapse eCRF page will be used. If such EDSS assessment is missing or not meeting the criteria to confirm the relapse, all other EDSS assessments taken

within 30 days from the relapse start date (i.e., EDSS assessment date – relapse start date  $\leq 30$ ) and before the relapse end date (EDSS assessment date  $<$  relapse end date) will be checked. If at least one of such available EDSS assessments meets the criteria, the relapse is a confirmed relapse. Otherwise, the relapse is considered an unconfirmed relapse.

- The time in study by subject will be used as an offset variable to adjust for the various length subjects have been observed (due to premature study discontinuation) and at-risk of a confirmed MS relapse in the study. Time in study for ARR will be calculated as (end of treatment period date – first dose date+1)/365.25.

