## 1 Introduction

The purpose of this Statistical Analysis Plan (SAP) is to describe the implementation of the statistical analysis planned in the protocol for study COMB157G2402.

There will be one report resulting from this SAP: the clinical study report (CSR) of the G2402 study. This report will be generated once and referred to as final CSR. The final CSR will be completed after the final database lock.

This document is consistent with the current study protocols (version 00 original protocol).

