## **2 Statistical methods**

### **2.1 Data analysis general information**

The Novartis statistical and programming teams will conduct the CSR analysis as planned in this SAP, unless otherwise specified.

The Statistical Analysis System (SAS) 9.4 and/or R 3.6.1 or higher versions will be used.

Unless otherwise stated, summary tables/figures/listings will be on all subjects in the respective analysis sets. Categorical data will be presented as frequencies and percentages. For continuous data, mean, standard deviations, median, 25th and 75th percentiles (optional), minimum and maximum will be presented.

For efficacy analyses other than MRI related analysis, all available data until the end of the Treatment Period, i.e. excluding the data collected during the Post-treatment Follow-up period, will be considered and no other cut-offs will be applied. For MRI related analysis, all available data from scheduled scans will be included, i.e. also including the ones taken in Post-treatment Follow-up period for the prematurely discontinued participants.

For safety analyses, unless otherwise specified, only data up to and including the safety cut-off of 100 days after the last administration of study treatment will be considered. Therefore, observations obtained beyond safety cut-off will be excluded from such analyses. Nevertheless, all serious adverse events (SAE) and all deaths, regardless of the safety cut-off will be summarized.

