Safety cutoff (off-treatment)	The safety cutoff is defined as 100 days after the last dose administration of study drug (or EOS for participants continue with commercial ofatumumab immediately after EOS, or min (last dose of study medication + 100 days, date of switching to another DMT - 1) for participants who have such switch in the Post-treatment Follow-up period). Unless

	explicitly otherwise stated, only data up to and including the safety cut-off will be included in the analysis and data beyond this time point for a given subject will be excluded. The safety cutoff applies to safety analyses only.
Nominal visits	Nominal visits are defined as all scheduled visits as per the clinical study protocol including the EOS visits. The definition of nominal visit excludes unscheduled visits.
End of Study (EOS)	EOS, used in the context of individual participants, refers to EOS visit.
End of treatment period date	This date is the date of discontinuation/study phase completion as recorded in the Study disposition eCRF page.
Last assessment on drug	It is the last assessment with non-missing value taken before or on the date of last administration of study drug. No visit windows will be needed for the identification of the last assessment on drug evaluation.

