### **2.5.3 Handling of missing values**

For participants who withdraw early from the study, the number of relapses up to the study discontinuation will be used for the primary analysis. No imputation will be applied to the incomplete study duration.

The primary negative binomial regression model with an offset for the time in study adjusts for missing information (drop-out) under the assumption of non-informative drop-out, information is missing at random, and constant relapse rate over time.

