### **2.5.4 Supportive analysis**

The primary analysis will be repeated based on all reported MS relapses (confirmed and unconfirmed) for FAS population.

ARR time-based and ARR participant-based will be provided for confirmed relapses and then for all relapses (confirmed and unconfirmed). ARRs using a “time-based approach” are calculated by taking the total number of relapses observed for all subjects divided by the total number of days in study of all subjects and multiplied by 365.25 days. “Participant-based approach” is calculated in the way where individual ARRs are computed and summarized over all subjects.

Listings of relapses along with their confirmation status (confirmed or unconfirmed) will be presented.

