## 4 Change to protocol specified analyses

Not applicable.

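### Should the primary ARR also count relapses after participants stop treatment, as the protocol's wording might suggest?

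*SAP*

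**What the plan says.** SAP 2.5.1 fixes both parts of the rate. The numerator is confirmed relapses with onset from first dose and "prior to or on the end of treatment period date will be included in the analysis". The denominator stops on the same day: "Time in study for ARR will be calculated as (end of treatment period date" less the first-dose date, plus one day, over 365.25). SAP 2.1.1 defines that date: "This date is the date of discontinuation/study phase completion as recorded in the Study disposition eCRF page". SAP 2.1 gives the general rule for efficacy data other than MRI: "excluding the data collected during the Post-treatment Follow-up period, will be considered and no other cut-offs will be applied".

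SAP 2.5.3, on early withdrawals, says that "the number of relapses up to the study discontinuation will be used for the primary analysis". This repeats Protocol 12.4.3. SAP 2.5.4 adds supportive rates: "ARR time-based and ARR participant-based will be provided for confirmed relapses and then for all relapses (confirmed and unconfirmed"). These vary the type of relapse and the method of calculation, but not the window.

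SAP section 1 states "This document is consistent with the current study protocols (version 00 original protocol"), and SAP section 4, on changes to protocol-specified analyses, reads "Not applicable".

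**The concern.** Three parts of the protocol can be read as promising more than the treatment-period rate.

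- Protocol 12.4.1 links the ARR estimate to intent-to-treat.
- The glossary and 9.1.1 keep stopping treatment apart from leaving the study. Someone who stops is still in the study unless consent is withdrawn.
- The opening of Protocol section 12 says that analyses take in follow-up data.

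Table 8-2 then schedules relapse assessment at EOS+3 and EOS+6 months, with monthly symptom interviews and an EDSS when relapse is suspected. Some relapses after stopping could therefore be confirmed.

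On that reading the SAP discards planned outcome data from early discontinuers, does not list this as a change, and in 2.5.3 keeps a phrase that seems to reach further than the formula in 2.5.1. The stake would be an ARR that looks too low if relapses rise once drug is withdrawn, in a study meant to support licence renewal.

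**Working it through.** **The plan's own figure.** Inputs from Protocol 12.8.1 and SAP 3.1: μ = 0.15, k = 0.82, n = 85, reference 0.30.

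- SE = √((μ + kμ²)/n) = √((0.15 + 0.82 × 0.0225)/85) = √(0.16845/85) = 0.0445.
- Range of the estimate: 0.15 ± 1.96 × 0.0445 = 0.063 to 0.237 (plan: 0.06 to 0.24).
- Probability that the upper limit is below 0.30: Φ(0.15/0.0445 − 1.96) = Φ(1.41) = 92.1%, as stated.
- Total N: 85/0.85 = 100, as stated.

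**The wording, side by side.**

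- *Within the SAP.* SAP 2.3.1 equates completing the study with completing the Treatment Period. It counts premature study discontinuation as leaving before that period ends, taken from the Study disposition page. Post-treatment Follow-up has its own disposition page. SAP 2.1.1 takes the end of treatment period date from the same Study disposition page. So the discontinuation named in 2.5.3 is the date used in 2.5.1, and the two sections agree.
- *Protocol 12.4.3* concerns people who withdraw early from the study. Under Protocol 9.1.1, someone who only stops treatment has not withdrawn, so the sentence does not settle what happens to that person's later relapses.
- *Protocol 12.4.1* attaches intent-to-treat most naturally to the FAS. In a single-arm trial it says who is analysed, not for how long.
- *The opening of Protocol section 12* sets no window for any endpoint. Protocol 12.5.2 goes on to cut safety data at 100 days, so the general sentence does not override endpoint rules.
- *Design basis.* The title says 12 months, the visit at treatment stop is called End of Study, and Protocol 12.8.1 takes the pivotal ARR from Month 0 to Month 12.

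**How much is left out.** Assumptions, not in the documents: 100 participants; a fraction p stop, at times spread evenly over Days 0 to 336; all are followed for 168 days after stopping, capped at Day 336. Mean added time per discontinuer is ½ × 168 + ½ × 84 = 126 days. The values of p are the planned 15% and the two pivotal dropout rates. The assumed post-stop rate r runs from 0 to 0.307, the teriflunomide rate in the sample-size section.

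- Counted = [100(1−p) × 336 + 100p × 168]/365.25
- Left out = 100p × 126/365.25
- ARR to Day 336 = (0.15 × counted + r × left out)/(counted + left out)

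| p | Counted (PY) | Left out (PY) | Share | ARR, r = 0.307 |
|---|---|---|---|---|
| 10.3% | 87.25 | 3.55 | 3.9% | 0.156 |
| 15% | 85.09 | 5.17 | 5.7% | 0.159 |
| 17.3% | 84.03 | 5.97 | 6.6% | 0.160 |

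At p = 15%:

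- r = 0 gives (0.15 × 85.09)/90.26 = 0.141.
- r = 0.15 leaves the ARR at 0.150.
- r = 0.307 gives (12.76 + 1.59)/90.26 = 0.159.
- The shifts are 0.0086/0.0445 = 0.19 and 0.0090/0.0445 = 0.20 of the design SE.
- With half of the discontinuers retained, the share left out is 2.59/87.68 = 3.0% and the ARR is 0.146 to 0.155.

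A harsher assumption, r = 0.60, has no source in the documents. It gives (12.76 + 0.60 × 5.17)/90.26 = 0.176, a shift of about 0.6 SE and still well under 0.30.

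**What a second window could show.** Expected post-stop relapses at p = 15% are 5.17 × 0.15 = 0.8 or 5.17 × 0.307 = 1.6. In 800 simulated trials per rate (gamma frailty with k = 0.82, intercept-only negative binomial model), there was no post-stop relapse in 50% and 23% of trials respectively.

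**The case for a change.** The strongest case for acting is that the protocol, read with its glossary, separates two kinds of discontinuation and the SAP merges them. SAP 2.1 keeps early discontinuers' follow-up scans for MRI but not their relapses, and gives no reason. Protocol 12.4.4 allows further sensitivity analyses, so one extra model run would cost little. Taken fully literally, a window running through all follow-up would add (15 × 168 + 85 × c × 168)/365.25 person-years, where c is the share of completers who do not continue on commercial drug. That is 6.9 (c = 0) to 46.0 (c = 1), with an ARR anywhere from 0.097 to 0.205 for r between 0 and 0.307.

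The difference in terminology is real, and SAP section 4 does not mention it. The rest carries less weight. The literal window goes beyond Month 12 and would mix treated time with off-drug time from only those completers who decline commercial ofatumumab. It does not match the objective or the sample-size basis, and c is not given. The MRI exception and the relapse rule stand together in SAP 2.1, which points to a deliberate choice.

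A supportive ARR to Day 336 also has a weakness. Protocol 9.1.1 asks discontinuers to attend where possible, accepts telephone contact otherwise, and sets the minimum data as treatments and adverse events. A confirmed relapse needs an EDSS. Time to last contact would therefore add denominator during which no relapse can be confirmed, and pull the rate down. Some of the time would also be on another MS therapy.

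**Conclusion.** No change follows. The SAP's rule is stated plainly, numerator and offset end together, and a relapse that leads someone to stop is still counted. It describes the rate over the treatment period, which is what the design and the Month 0 to Month 12 reference call for. The mismatch with the protocol's glossary is one of terms. A line in section 4 would tidy the record but alter no number.

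Under the stated assumptions, about 4% to 7% of person-time is left out, and the ARR moves by about 0.2 of the design SE for post-stop rates between 0 and 0.307. The direction is not known in advance, because drug is withdrawn but other therapy may begin. Protocol section 12 plans no hypothesis test, and no reading confined to Day 336 brings the estimate near 0.30. An extra analysis would often rest on no post-stop relapse or only one or two, so it could not test whether drop-out is informative.

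This rests on discontinuation near the planned 15% and on the readable text; Protocol 12.6 and SAP 2.12 are redacted. Much heavier early stopping, or a post-stop rate far above 0.307, would enlarge the gap between the two windows.

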### 2.1.2.2 Visit windows after study drug discontinuation

For summaries of data collected after study drug discontinuation, data from both Treatment period and Post-treatment Follow-up period will be considered. All reporting will be done based on visit windows defined relative to the last administration of study drug.

The visit window definitions are provided in [Table 2-8](#) where the Start day and End day are relative to the date of last administration of study drug. For the “Last assessment on drug”, the last assessment with non-missing value taken before or on the date of last administration of study drug will be summarized (no visit window applies). For the “Month 3 after LDD (last dose date)” visit-window, assessments taken at least 1 day after but no more than 126 days after the date of last administration of study drug will be considered. LDD stands for last dose date and will be footnoted in applicable output(s).

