#### 5.1.4.2 Relapse date imputation

Missing or partial dates are not expected for the start and end dates of relapses on the Summary of MS relapse CRF pages. In case partial dates (unknown day with month and year available) exist in the final database, the following rules will apply:

- The start date will be imputed as the first day of the month or the first dose date if it occurs in the same month as the first dose date.
- The end date will be imputed as the last day of the month or truncated to have a duration of maximally 90 days (whatever comes first).

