#### 5.1.4.3 Data handling for relapses within 30 days of onset of previous relapses or relapses with duration beyond 90 days

According to the protocol definition of MS relapses, the start date of a new relapse has to be at least 30 days after the start date of a previous relapse (i.e. start date of a new relapse – start date of a previous relapse  $\geq 30$ ). If a relapse is recorded with a start date  $< 30$  days after the start date of a previous relapse, the below data manipulation will be done to combine them into a single relapse by creating a new relapse record with the following information:

- Start date: Take the earliest start date.
- End date: Take the latest end date. If one of the end dates is missing, set it to missing.
- Date of EDSS intended to confirm the relapse:
  - Take the date of EDSS by which the relapse can be confirmed.
  - If more than one EDSS assessments meet the above criterion, take the date of the EDSS from which the worst severity value is derived.
  - If no EDSS assessment meets the above criterion, take the earliest date of EDSS as captured on the Summary of MS Relapse CRF page.
- Severity: Take the value representing the worst case (severe > moderate > mild > missing) (as specified in [Table 5-1](#))
- “Hospitalization?”, “Steroid used?”, “Recovery status”: For each of these characteristics, take the value representing the worst case (yes > no for the first 2 questions; no > partial > complete recovery for the last question).

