**Table 5-1 Severity of MS relapses ([Panitch et al 2002](#))**

Mild relapse	Moderate relapse	Severe relapse
EDSS increase of 0.5 point	EDSS increase of 1 or 2 points	Exceeding moderate criteria
or	or	Or
1-point FS change in one to three systems	2-point FS change in one or two systems	Exceeding moderate criteria
	or	Or

	1-point change in four or more systems	Exceeding moderate criteria
Definition is based on the EDSS obtained to confirm the relapse as compared to the last EDSS (scheduled or unscheduled) taken in the absence of (confirmed or unconfirmed) relapse and prior to the current relapse.		
EDSS refers to total score; FS refers to functional score; all of the 7 functional scores are considered in this derivation.		

According to the protocol definition of MS relapses, the maximum duration of a relapse is furthermore limited to 90 days. If a relapse is recorded with a duration longer than 90 days, the end date will be truncated to have a duration of exactly 90 days. This applies also to the artificial records created by the above procedure. Missing end date of relapse is not allowed. In the rare cases that missing end date exists in the final database, it will be imputed so that the duration of relapse is exactly 90 days.

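### SAP 2.5.1: the fallback search for a confirming EDSS has no lower date limit, so as written a score from an earlier relapse can confirm a later one

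*SAP*

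**What the plan says.** The number of confirmed relapses per participant is the response variable of the primary negative binomial model (SAP 2.5.1 and 2.5.2). SAP 2.5.1 confirms a relapse when the EDSS rises by at least 0.5, or when one of two functional-score criteria is met, "compared to the last EDSS assessment taken in the absence of (confirmed or unconfirmed) relapse and prior to the current relapse". The score tested first is the one dated on the relapse eCRF page.

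The fallback then reads: "If such EDSS assessment is missing or not meeting the criteria to confirm the relapse, all other EDSS assessments taken" in a stated window are checked. The window is "within 30 days from the relapse start date (i.e., EDSS assessment date – relapse start date", with that difference at most 30, and the EDSS date must also fall before the relapse end date. One score is enough: "If at least one of such available EDSS assessments meets the criteria, the relapse is a confirmed relapse".

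Two other rules matter here. SAP 5.1.4.3 merges relapses only when their onsets are less than 30 days apart, because "the start date of a new relapse has to be at least 30 days after the start date of a previous relapse". Protocol 8.3.1, to which Protocol 12.4.1 refers for confirmation, requires the EDSS change to accompany the relapse. It has no fallback search and no date window.

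**The concern.** The fallback exists to rescue a relapse whose designated score was missing or uninformative by finding another score from the same relapse. That needs a window that opens at onset. The formula only closes the window, at 30 days after onset or at the relapse end. A negative difference always satisfies a limit of at most 30, so the whole pre-onset history is eligible.

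The phrase about being prior to the current relapse does not help, because it dates the reference score and not the score under test. SAP 5.1.4.2 and 5.1.4.3 add no limit either. Where the SAP wants both ends of a window it can state them: SAP 2.1.2.2 takes "assessments taken at least 1 day after but no more than 126 days after the date of last administration of study drug".

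At stake is the primary event count. A program that follows the formula exactly could count as confirmed a relapse with no EDSS evidence of its own.

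**Working it through.** **1. The rule as written, on constructed records.** Reference EDSS 2.5 on Day 84. Relapse A starts on Day 100, with EDSS 3.5 on Day 110. Relapse B starts on Day 135 and ends on Day 160, with designated EDSS 2.5 on Day 140. The onsets are 35 days apart, so SAP 5.1.4.3 does not merge them. The next scheduled visit after Day 84 is Day 168 (Protocol Table 8-1), so no scheduled relapse-free EDSS falls between A and B.

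- B's own score: 2.5 − 2.5 = 0, not confirming, so the fallback is triggered.
- A's score tested for B: 110 − 135 = −25, which is ≤ 30; Day 110 is before Day 160; 3.5 − 2.5 = +1.0, which is ≥ 0.5.

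| Reading of the window | A's Day 110 score confirms B? |
|---|---|
| As written (difference ≤ 30) | Yes |
| Plus or minus 30 days | Yes |
| 0 to 30 days | No |

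Two controls behave as they should under all three readings. If the only pre-onset score is the reference itself, the change is 0 and nothing is confirmed. If B has a further EDSS of 3.0 on Day 150 (difference 15, change +0.5), B is properly confirmed.

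**2. The plan's own precision.** With μ = 0.15, k = 0.82 and n = 85 (Protocol 12.8.1, SAP 3.1), SE = √((0.15 + 0.82 × 0.15²)/85) = 0.0445. The 95% range is 0.15 ± 1.96 × 0.0445 = 0.063 to 0.237. The probability that the upper limit is below 0.30 is Φ(0.15/0.0445 − 1.96) = 0.921. The plan states 0.06 to 0.24 and 92.1%, so its figures reproduce.

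**3. Effect of one false confirmation.** Assume that 85 of 100 participants complete 336 days and that 15 stop, on average, at 168 days. Person-years = (85 × 336 + 15 × 168)/365.25 = 85.09. Expected confirmed relapses = 0.15 × 85.09 = 12.8. One extra event adds 1/85.09 = 0.012 to the crude ARR. That is 0.01175/0.15 = 7.8%, or 0.01175/0.0445 = 0.26 of the planning SE.

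**4. How often it could happen.** The documents give no frequency, so this step rests on assumptions.

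- *Two or more relapses.* Take a negative binomial with k = 0.82, mean = rate × 0.851 years, and an assumed rate of all reported relapses of 0.15 to 0.30. Then P(≥ 2) = 0.012 to 0.039, or 1.2 to 3.9 participants in 100.
- *No relapse-free scheduled EDSS between them.* Take EDSS on Days 28, 84, 168, 252 and 336 (Protocol 8.3.3 with Table 8-1), and two onsets placed uniformly over 336 days, at least 30 days apart. By simulation, the share with no scheduled visit between the end of A and the onset of B is about 26% if A lasts 30 days, 10% if 0 days, and 57% at the 90-day cap in SAP 5.1.4.3.
- *Product.* At 30 days: 1.2 × 0.26 = 0.3 to 3.9 × 0.26 = 1.0 participants. Over the range of durations: 1.2 × 0.10 = 0.1 to 3.9 × 0.57 = 2.2.

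These counts come before three further conditions: A's score must be high enough, B's own score must be missing or fail, and no valid score after B's onset may already confirm it. Each lowers the number.

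**The case against.** The strongest reply is that the text around the formula already fixes the order. Both documents speak of a relapse accompanied by an EDSS increase, Protocol 8.3.1 places the examination after the participant reports symptoms, and scores within 30 days from onset are naturally read as later scores. On this view the formula is shorthand and a sensible programmer would start at onset. That stands as a statement of likely intent. It does not remove the defect, because the SAP introduces the formula as the meaning of the phrase. Reading the phrase as plus or minus 30 days does not cure it either, as the example shows.

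It also stands that the route needs several coincidences, that the error can only work against the drug, and that SAP 2.5.4 repeats the analysis on all reported relapses and lists each with its confirmation status. Those outputs would expose a case but leave the primary ARR unchanged.

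A reader might infer that any older, higher score, such as a screening value above a later reference, would also confirm a relapse. The documents do not support that. Confirmation requires an increase from the last relapse-free score, and a higher value before that reference is followed by a decrease. It would pass only if a programmer ignored time order.

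**Conclusion.** Wrong as written, and minor. Followed literally, SAP 2.5.1 lets a raised EDSS from an earlier, unmerged relapse confirm a later relapse that its own EDSS did not confirm. Under the assumptions above this concerns roughly 0 to 1 participant in 100. Each event would add about 0.012, or about 8%, to an expected ARR of 0.15. The size depends on the assumed relapse rates, relapse durations and dropout pattern.

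Two stronger conclusions are tempting and should not be drawn.

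- *That the 92.1% probability of an upper limit below 0.30 is materially eroded.* That would require false events in every replicate of the trial, which the frequency estimate does not support. The 92.1% is also a natural-scale planning figure, whereas the fitted model has a log link, and Protocol section 12 plans no hypothesis test.
- *That relapse severity results would be distorted.* SAP Table 5-1 does say "Definition is based on the EDSS obtained to confirm the relapse as compared to the last EDSS", so the wrong score could supply the grade. But severity is used only in the merge rule of SAP 5.1.4.3, and SAP 2.5.4 plans no summary by severity.

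**What to change.** In SAP 2.5.1, state the fallback window as 0 ≤ EDSS assessment date − relapse start date ≤ 30, and EDSS assessment date < relapse end date.

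The lower limit should not reject valid scores. For partial dates, "The start date will be imputed as the first day of the month or the first dose date" where that falls in the same month, so the imputed onset is not later than the true one. Merged relapses take the earliest start date (SAP 5.1.4.3).

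The cost is one inequality in the SAP and the matching line in the derivation program. No new data, visits or analyses are needed.
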